10.1.3. Safety Analysis Set

The Safety Analysis Set includes all enrolled subjects who receive at least one dose of TPX-0046. Each subject will be classified into and analyzed consistently within one treatment group.

10.2. Sample Size Determinations

10.2.1. Phase 1 Dose Escalation

For Phase 1 dose escalation, 41 subjects have enrolled across 9 dose levels. Enrollment is closed.

10.3. Statistical Analysis

10.3.1. General Considerations

10.3.1.1. Software

All data listings, summaries and statistical analyses will be generated using SAS® Version 9 or above, or equivalent statistical software.

10.3.1.2. Missing Data

All analyses and descriptive summaries will be based on the observed data. Unless otherwise specified missing data will not be imputed. Partial dates for AEs and concomitant medications will be imputed using the most conservative rules.

10.3.1.3. Baseline Measurements

The last measurement on or prior to the date of the first dose will serve as the baseline measurement and should be within 28 days of first dose.

10.3.1.4. Data Presentation

Categorical variables will be summarized in frequency tables, with the counts and percentage of subjects in each category. Percentages given in the summary tables will be rounded and thus may not always add up to exactly 100 percent. For continuous variables, summary statistics will include N, mean, standard deviation, median, and minimum and maximum values (range).

10.3.1.5. **Duration**

Duration, except for duration of treatment, is calculated as:

Duration (days): (End Date – Start Date + 1)

Duration (weeks): (End Date - Start Date + 1)/7

Duration (months): (End Date - Start Date + 1)/30.4375*

Duration (years): (End Date - Start Date + 1)/365.25**

10.3.2. Subject Disposition

A disposition table will summarize the number of subjects enrolled, treated, discontinued from study treatment and the reasons for treatment discontinuation, and end-of-study and reasons. The reason for discontinuation and end-of-study will be summarized using the categories specified in the Study Discontinuation, and End-of-Study CRF page, by cohort.

10.3.3. Demographics and Baseline Characteristics

Demographics and baseline characteristics including disease staging, histology, smoking history, ECOG performance status, CNS metastasis at baseline, prior treatment history, and molecular diagnostic test results on oncogenic *RET* fusions or mutations will be summarized from the CRF data for all subjects in the FAS by cohort.

10.3.4. Efficacy Analyses

Radiologic assessments evaluated by the Investigator will be explored for Phase I in efficacy analysis set. Number of subjects with ORR will be summarized.

10.3.4.1. Objective Response Rate

The ORR will be defined as the proportion of subjects with a confirmed complete response (CR) or partial response (PR). A confirmed response is a response that persists on a repeat imaging performed at least 4 weeks after initial documentation of response. Subjects with a confirmed objective response (CR or PR) will be referred to as responders. Non-responders will include subjects without a confirmed objective response, stable disease (SD), progressive disease (PD), not evaluable (NE), or non-CR/non-PD (NN).

10.3.5. Safety Analyses

Safety analyses will be performed using the Safety Population for each cohort, as well as for all cohorts combined.

10.3.5.1. Extent of Exposure

Exposure analysis will be based on the actual dose administered for the investigational product. Duration of treatment will be calculated as the last dose date minus the first dose date plus one day. Duration of treatment and total daily dose amount will be summarized using descriptive statistics. The number of subjects treated by cycles will be summarized.

10.3.5.2. Adverse Events

AEs will be graded according to the CTCAE version 5.0 and coded to preferred term and system organ class using the MedDRA version 21.1 or higher.

^{*}Average number of days in a month = 30.4375, which is based on 365.25/12 where 365.25 represents the average number of days in a year and 12 represents the number of months in a year

^{**}Average number of days in a year = 365.25, reflecting the Julian Year of three years with 365 days each and one leap year of 366 days.

All AEs reported during the AE reporting period (inclusive AEs after the post last dose of the investigational product) will be considered as treatment-emergent adverse events (TEAEs).

For the dose escalation phase, the number of subjects with DLTs by dose level will be listed.

Incidence rates will be summarized with frequency and percentage by MedDRA SOC and preferred term. In addition, AE incidence rates will also be summarized by severity and relationship to investigational product. Treatment-related AEs are those judged by the Investigator to be at least possibly related to the investigational product. Subjects with multiple occurrences of events will be counted only once at the maximum severity to investigational product for each preferred team, SOC, and overall. Deaths that occur within 28 days after the last dose of the investigational product are defined as on-study deaths and reported as SAEs within the required reporting period.

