4.1.1.1. Dose Escalation Schema

The dose escalation schema is illustrated in Table 5. No further dose escalation will occur; dose level 9 was the last to enroll subjects prior to closing study enrollment. DLTs will be evaluated independently in any given dosing regimen.

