6. STUDY TREATMENT

6.1. Allocation to Treatment

All subjects will be allocated to receive TPX-0046. For the Phase 1 dose-escalation portion of the study, subjects will be assigned according to the currently open dosing level at the time of enrollment.

Dose level allocation will be performed by the Sponsor after subjects have given their written informed consent and have completed the necessary baseline assessments. The site staff will complete a Registration Form for the designated Sponsor study team member or designee. The Sponsor will assign a subject identification number and supply this number to the site. The subject identification number will be used on all study related documentations at the site.

No subject shall receive TPX-0046 until the Investigator or designee has received the following information in writing from the Sponsor:

- Confirmation of the subject's enrollment;
- Specification of the dose level for that subject and;
- Permission to proceed with dosing the subject.

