6.2. Investigational Product Supplies

6.2.1. Dosage Forms and Packaging

The investigational TPX-0046 drug product is supplied as capsules (Table 10). TPX-0046 capsules are capsules manufactured for use in the proposed clinical program. High-density polyethylene

(HDPE) bottles induction sealed with child resistance caps were selected as the container closure. TPX-0046 will be supplied in bottles containing 30 capsules of a single strength. TPX-0046 will be supplied by the Sponsor. See the Investigator's Brochure for details on the original and new formulations.

Table 10: TPX-0046 Investigational Product

Product Name:	TPX-0046
Dosage Form:	Capsules
Unit Dose:	
Route of Administration:	Oral
Physical Description:	

NOTE: Drug product will not be available past July 2023.

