9.3. Reporting of Adverse Events and Serious Adverse Events

9.3.1. Reporting of Adverse Events

Adverse event data will be collected from the time of first dose until 28 days after last dose.

All AEs, whether believed by the Investigator to be related or unrelated to the investigational product, must be documented in the subject's medical records, in accordance with the Investigator's normal clinical practice and on the AE CRF. Each AE is to be evaluated for duration, intensity, frequency, seriousness, outcome, other actions taken, and relationship to the investigational product. Redacted medical record source documents will be requested for all SAEs and emergency room visits.

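### TEAE percentages by dose level cover unequal time at risk, so differences in later-onset events may partly reflect length of follow-up rather than dose (minor)

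*Combined protocol and SAP*

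**What the plan says.** Section 10.3.5.2 (Adverse Events) treats all AEs in the reporting period as treatment-emergent and plans that "Incidence rates will be summarized with frequency and percentage by MedDRA SOC and preferred term". The counting rule is that "Subjects with multiple occurrences of events will be counted only once at the maximum severity". The reporting period is in Section 9.3.1: "Adverse event data will be collected from the time of first dose until 28 days after last dose".

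On grouping, Section 10.3.5 says: "Safety analyses will be performed using the Safety Population for each cohort, as well as for all cohorts combined". Section 10.1.3 adds: "Each subject will be classified into and analyzed consistently within one treatment group". The text does not define a cohort for dose escalation; it is read here as a dose level.

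On how subjects reached a level, Section 6.1 says that "subjects will be assigned according to the currently open dosing level at the time of enrollment", and Section 4.1.1.1 that "dose level 9 was the last to enroll subjects prior to closing study enrollment". Section 8.3 lets treatment end when alternative care becomes possible, besides progression, toxicity and withdrawal of consent. Section 6.2.1 states: "NOTE: Drug product will not be available past July 2023".

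Section 10.3.5.1 summarises treatment duration and the number of subjects treated by cycle. It does not link either to the AE percentages. Section 10 plans no person-time figure, time-to-event method or common-window table for TEAEs. It leaves detailed methods to a SAP, and the text supplied contains no separate SAP section on this point.

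**The concern.** The quantity that the plan calls an incidence rate is a proportion: subjects with at least one event divided by subjects treated. Such a proportion grows with the time over which a subject can have a first event. If every level had much the same time at risk, this would not matter for reading across the columns. Here the calendar works against that. Early levels had a longer possible treatment time than the last one, and the closure of development adds two ways of stopping that have nothing to do with tolerability. Toxicity itself can act in the same direction: a regimen that drives subjects off drug early leaves fewer months in which a later event can be recorded.

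At stake is the descriptive reading of tolerability by regimen in the synoptic report, mainly for events that start after Cycle 1.

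**Working it through.** **Is there a plan figure to reproduce?** No. The documents give no TEAE rate, treatment duration by level or enrolment date, so the calculations below show the mechanism and its possible range only.

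**Step 1: the calendar.** Sites were told of the stop on 03 October 2022 (Section 3), and drug is not available past July 2023 (Section 6.2.1). Counting both end dates, 03 October 2022 to 1 July 2023 is 272 days, and to 31 July 2023 it is 302 days.

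- 272 / 30.4375 = 8.9 months; 302 / 30.4375 = 9.9 months
- 272 / 28 = 9.7 cycles; 302 / 28 = 10.8 cycles

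If enrolment ended on 03 October 2022 at the latest (an assumption), a subject who started that day could be treated for at most about 10 months. Anyone who started earlier had a higher ceiling. The supply limit matters only for subjects still on drug when it is reached; a move to alternative care can shorten treatment sooner.

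**Step 2: effect on a crude percentage when dose has no effect.** Assumptions, none from the documents: the same constant hazard h per month of a first event at every level; treatment time exponential with median m months, so μ = ln 2 / m; an administrative ceiling of C months; and a 28-day tail f = 28 / 30.4375 = 0.92 months. Then

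crude proportion = 1 − exp(−h·f) × { μ/(μ+h) × [1 − exp(−(μ+h)C)] + exp(−(μ+h)C) },

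and with no ceiling, 1 − exp(−h·f) × μ/(μ+h).

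Worked case, m = 6 and h = 0.05: μ = 0.1155, exp(−h·f) = 0.955 and μ/(μ+h) = 0.698.
- No ceiling: 1 − 0.955 × 0.698 = 33.3%.
- C = 9.9: exp(−0.1655 × 9.9) = 0.194, so 1 − 0.955 × (0.698 × 0.806 + 0.194) = 27.7%.

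| m (months) | h per month | No ceiling | C = 9.9 | C = 6 | C = 3 |
|---|---|---|---|---|---|
| 3 | 0.05 | 21.5% | 20.4% | 18.3% | 14.2% |
| 6 | 0.05 | 33.3% | 27.7% | 22.7% | 15.8% |
| 12 | 0.05 | 48.8% | 33.6% | 25.6% | 16.7% |
| 12 | 0.10 | 66.6% | 54.5% | 44.2% | 30.6% |

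Over m = 3, 6, 12 and h = 0.02, 0.05, 0.10, 0.30, the gap between no ceiling and 9.9 months runs from 0.2 points (m = 3, h = 0.30: 67.0% against 66.8%) to 15.2 points (m = 12, h = 0.05). Early levels also meet the July 2023 limit, only later in treatment, so the no-ceiling column overstates the contrast from supply alone. The shorter ceilings stand for earlier moves to alternative care.

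**Step 3: what a fixed window gives.** Under the same hazards the risk in the first 28 days is 1 − exp(−h·f): 4.5% at h = 0.05 and 8.8% at h = 0.10, equal at every level. Because AEs are collected for 28 days after the last dose, even a subject who takes a single dose contributes a full 28 days, barring death, loss to follow-up or withdrawn consent.

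**Step 4: set against sampling error.** 41 / 9 = 4.6 subjects per level on average. The worked case, 33.3% against 27.7%, is 1.5 against 1.3 subjects. An observed 2 of 5 has an exact 95% interval of 5.3% to 85.3%.

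**The case against.** Four points can be made for the plan, and each has force.

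- **The dose-finding endpoint is already on a common window.** First-cycle DLTs are the primary safety endpoint. They are assessed over 28 days (Section 4.1.1.2) and listed by dose level (Section 10.3.5.2), and the MTD is defined on Cycle 1 (Section 4.1.1.3). This stands in full. It does not cover toxicity below the DLT threshold or onset after day 28.
- **No comparison of levels is planned.** The TEAE tables are descriptive, with no test, trend or ranking. True, but a table with one column per level will be read across.
- **Exposure and reasons for stopping are reported.** Section 10.3.5.1 gives duration and subjects by cycle, and Section 10.3.2 gives discontinuation reasons by cohort. A careful reader can set these beside the percentages. This softens the point without removing it, since treatment duration is not time at risk (the 28-day tail is missing) and the two are never put together.
- **Small numbers dominate.** Step 4 confirms this. It limits the weight of the concern, though noise does not cancel a systematic difference.

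A reader might also infer that event rates per patient-month are the right basis for comparing levels. The documents give no ground for the constant hazard this needs, and the method can create the very error it is meant to remove. Suppose (assumed) that 40% of subjects at every level have the event at month 1 and none later. With 3 months of follow-up the rate is 0.4 / (0.4 × 1 + 0.6 × 3) = 0.4 / 2.2 = 0.18 per month. With 12 months it is 0.4 / (0.4 × 1 + 0.6 × 12) = 0.4 / 7.6 = 0.053. That is a false difference of about 3.5-fold where the crude percentages agree.

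**Conclusion.** The concern holds in a limited form. Percentages by level for later-onset TEAEs may partly reflect time at risk, because possible treatment time differs by level for reasons unrelated to toxicity and the planned table does not show it. DLT incidence and the MTD are not affected, and early-onset events are little affected. The conclusion rests on reading a cohort as a dose level and on treatment durations that really do differ between levels; the second cannot be checked from the documents. Severity is minor.

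Three stronger readings are tempting and not supported:

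- **That the primary safety result or the decision to stop development is undermined.** The primary safety endpoint uses a fixed window. Section 3 rests the stop on the totality of clinical information, and sites were told in October 2022, before any final TEAE table.
- **That a large spread can be expected in this trial.** A constant hazard of 0.10 per month gives 26% at 3 months and 70% at 12, but only by assigning those follow-up times to levels. The documents assign none.
- **That a low TEAE percentage at level 9 would be a follow-up artefact.** Level 9 was the last to enrol and is also a lower-dose regimen than the levels just before it. Without durations the two explanations cannot be separated.

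**What to change.** Keep the planned TEAE table. In Section 10.3.5.2:

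1. Add a table by dose level of subjects with TEAE onset in the first 28 days, for all TEAEs, grade 3 or higher, and treatment-related. Count from the first dose of the assigned regimen in Cycle 1, as the DLT window does.
2. Print total person-time at risk by level (first dose to 28 days after last dose, or end of observation if earlier) beside the whole-period table.
3. Base any descriptive statement comparing regimens on the 28-day table, with a footnote that levels 5 and 7 to 9 spend the first 14 days at their starting dose, so half of that window precedes the later dose.
4. Treat rates per patient-month as optional and supportive, with the constant-hazard assumption stated.

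Section 10.3.5 should also say that a cohort means a dose level.

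The cost is one extra table and one added row, from dosing and AE onset dates that the planned analyses already use, with no change to conduct. The downsides are small counts per level and no information on late-onset events from the 28-day table; for those, the whole-period table read with its person-time remains the only source.

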11. QUALITY CONTROL AND QUALITY ASSURANCE

It is the Investigator's responsibility to ensure the accuracy, completeness, and timeliness of the data reported for each subject. Source documentation supporting the data should indicate the subject's participation in the study and should document the dates and details of study procedures, AEs, and subject status.

To ensure compliance with Good Clinical Practice (GCP) and all applicable regulatory requirements, the Sponsor may conduct a quality assurance audit.

12. DATA HANDLING AND RECORD KEEPING

12.1. Case Report Forms/Electronic Data Record

After data have been entered into the study database, a system of computerized data validation checks will be implemented and applied to the database on a regular basis. Queries will be entered, tracked, and resolved directly through the electronic data capture (EDC) system. The study database will be updated in accordance with the resolved queries. All changes to the study database will be documented.

12.2. Study Monitoring, Audits, and Inspections

Site visits will be conducted by an authorized Sponsor representative, who will inspect study data, subjects' medical records, and CRFs according to GCP, the FDA, and the International Conference on Harmonisation (ICH) guidelines. In addition to monitoring by the Sponsor or its designees, the study may be audited by representatives of the FDA or other regulatory authorities, who will also be permitted access to study documents. The Investigator should immediately notify the Sponsors' Clinical Operations department or designee of any proposed or scheduled audits by regulatory authorities.

The Investigator will permit authorized representatives of the Sponsor or designee and national or local health authorities to inspect facilities and records relevant to this study.

The Investigator must obtain Institutional Review Board (IRB)/IEC approval for the investigation. Initial IRB/IEC approval and all materials approved by the IRB/IEC for this study,

including the subject consent form and recruitment materials, must be maintained by the Investigator and made available for inspection.

12.3. Inspection of Records

The Sponsor and designees of the Sponsor will be allowed to conduct site visits to the investigational facilities for monitoring any aspect of the study. The Investigator agrees to allow Sponsor representatives to inspect the drug storage area, investigational product inventory, drug accountability records, subject charts and study source documents, and other records relative to the study conduct.

12.4. Record Retention

The Investigator will coordinate with the study site to ensure all documentations relating to the study for a period of 2 years after marketing application approval or, if not approved, 2 years after the notification to the FDA of the discontinuance of the investigational product for investigation. If it becomes necessary for the Sponsor or the Regulatory Authority to review any documentation relating to the study, the Investigator must permit access to such records.

The records should be retained by the Investigator according to ICH, local regulations, or as specified in the Clinical Trial Agreement, whichever is longer; but at a minimum, all study documentation must be retained for 2 years after the last marketing application approval in an ICH region or after at least 2 years have elapsed since formal discontinuation of clinical development of TPX-0046.

13. ETHICS

13.1. Ethics Review

The final study protocol, including the final version of the ICF, must be approved or given a favorable opinion in writing by an IRB/IEC, as appropriate. The Investigator must submit written approval to the Sponsor before he or she can present informed consent and begin screening activities for any subject in the study.

The Investigator is responsible for informing the IRB/IEC of any amendment(s) to the protocol in accordance with local requirements. In addition, the IRB/IEC must approve all advertising used to recruit subjects for the study, if applicable. The protocol must be re approved by the IRB/IEC upon receipt of amendments and annually, as local regulations require.

The Investigator is also responsible for providing the IRB/IEC with reports of any reportable serious adverse drug reactions from any other study conducted with the investigational product. The Sponsor will provide this information to the Investigator.

Progress reports and notifications of serious adverse drug reactions will be provided to the IRB/IEC according to local regulations and guidelines.

13.2. Protocol Compliance

The Investigator will conduct the trial in compliance with the protocol provided by the Sponsor. Modifications to the protocol may not be made without agreement of both the Investigator and

the Sponsor. Changes to the protocol will require a written IRB/IEC approval/favorable opinion before implementation, except when the modification is needed to eliminate an immediate hazard(s) to subjects. The IRB/IEC may provide, if applicable, regulatory authority(ies) permit, and expedited review and approval/favorable opinion for minor change(s) in ongoing trials that have the approval/favorable opinion of the IRB/IEC.

When immediate deviation from the protocol is required to eliminate an immediate hazard(s) to subjects, the Investigator will contact the Sponsor/Designee and/or the Study Monitor, if circumstances permit, to discuss the planned course of action. Any departures from the protocol must be fully documented on the appropriate CRF and in the source documentation and reported to the IRB/IEC per institutional and/or local requirements.

13.3. Ethical Conduct of the Study

The study will be performed in accordance with ethical principles that have their origin in the Declaration of Helsinki and are consistent with ICH/GCP, applicable regulatory requirements, and the Sponsors' (or its designee's) applicable policies and standard operating procedures (SOPs).

13.4. Written Informed Consent

The Investigator at the study center will ensure that the subject is given full and adequate oral and written information about the nature, purpose, possible risk(s), and benefit(s) of the study. Subjects must also be notified that they are free to withdraw from the study at any time. The subject should be given the opportunity to ask questions and allowed time to consider the information provided.

The subject's signed and dated ICF must be obtained before conducting any study procedures.

The Investigator must maintain the original signed ICF. A copy of the signed ICF must be given to the subject.

